Vocal cord cyst is a fluid-filled sac inside the vocal cord, with 2 subtypes: 1) Epidermoid cyst due to epithelial inclusion 2) Mucous retention cyst due to glandular ductal obstruction. Vocal cord cysts typically do not resolve with voice therapy, and are traditionally excised with microlaryngeal surgery with microflap technique or marsupialization. ^(6,7) In our previous RCT study, subgroup analysis did not show a significant difference of vocal cord cyst recurrence in both TNLS and MLS group. However, our cohort had a higher overall vocal cord cyst recurrence rate (13.8%) compared to historic cohort rate of 2.2-8.7%^(5, 8), which may be accounted by that our vocal cord cysts were ablated and marsupialized instead of removed in the TNLS group. Nevertheless, a recent case series by Gao and colleagues showed a good functional outcome of awake KTP-laser marsupialization in selected cases. ⁹ A larger cohort is warranted to compare TNLS to MLS for vocal cord cyst. Therefore, our authors would like to conduct a randomized controlled trial to compare tradition MLS surgery to TNLS, with hypothesis that TNLS would be non-inferior to traditional microlaryngeal surgery in benign laryngeal lesions, and with its additional benefits on minimization of anesthetic risks and hospital expenses, hopefully to expand its further application.

Methodology

Study setting

This is a prospective, single-cluster randomized controlled trial conducted at two tertiary referral hospitals (Prince of Wales Hospital and Alice Ho Miu Ling Nethersole Hospital, NTEC) in Hong Kong to compare the clinical and functional outcomes of office-based TNLS to traditional microlaryngeal surgery under general anesthesia for vocal cord cysts.

Eligibility criteria

All consecutive patients with vocal cord cysts interested in operative management will be screened for eligibility.

Inclusion criteria

Patients who are (i) older than 18-year-old; (ii) able to independently provide consent; and (iii) able to tolerate flexible laryngoscopy would be recruited.

Exclusion criteria

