2. Complete head and neck physical examination
3. Flexible laryngoscopy for confirmation of diagnosis, with photo documentation of site and size (in relative to length of vocal cord in full abduction)

Diagnosis would be explained to patients, and management options of conservative, microlaryngeal surgery under general anesthesia, and TNLS with their pros and cons would be discussed. Patient information sheet and informed consent are provided to facilitate the

process. Should the patient decide to participate in the study, consent of the study would be signed in the same clinic session. Patient would be informed of his randomized treatment group, and consent of the surgery would be also signed in the same section. Participation is voluntary and any study subject can decide to withdraw at any time of the study period. Upon study withdrawal, the patient will continue to receive standard treatment according to disease status.

In addition to above mentioned assessments, patient would also be assessed in a multidisciplinary voice clinic undergoing a detailed voice assessment co-organized with speech language pathologist, including Voice-Handicap Index (VHI-30), perceptual evaluation of voice, acoustic voice analysis, aerodynamic measures and laryngeal imaging.

Failure of study intervention

When patients cannot tolerate the allocated intervention, for example patients randomized to MLS group but contraindicated to general anesthesia, or patients randomized to TNLS but cannot tolerate transnasal laser surgery due to discomfort or anxiety, can crossover to other study arm. Outcomes would be analyzed by intention-to-treat principle.

Follow-up schedule

All patients would have follow-up in a multi-disciplinary voice clinic on post-op 2 weeks, 6 weeks, 3 months, 6 months and 1 year. During the postoperative follow-ups, patients are required to fill in a questionnaire and undergo voice assessments as mentioned above.

Primary outcome

The primary outcome was to compare the pre- and post-operative Voice-Handicap Index (VHI-30) of TNLS and MLS groups. The VHI-30 is a 30-item self-administered questionnaire, which has been shown to be a reliable measure for voice treatment outcome.^(10,11) It consists of three subscales, namely physical, functional and emotional. It provides an overall measurement of a person's vocal function and how it influences a person's everyday functioning and experience.

Secondary outcomes

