The secondary outcomes included other voice-related outcomes (i.e. perceptual analysis, acoustic voice analysis, aerodynamic measure, visual analog scale (VAS) on voice quality), procedure-oriented outcomes, patient-oriented outcomes and hospital costs. Perceptual evaluation of voice using the GBRAS scale, in which patients would be required to produce sustained vowel and connected speech voice samples. Two experienced speech-language pathologists blinded to the patient's information would rate the audio recordings. For acoustic voice analysis, it would be conducted using PRATT program with parameters including

jitter, shimmer, noise-to-harmonic ratio measures and cepstral peak performance. For aerodynamic measure, maximal phonation time (MPT) would be measured by instructing patients to phonate /a:/ sound for as long as possible after maximal inspiration, at a spontaneous, comfortable pitch and loudness level, for three consequent trials. In VAS, patients would be asked to self-rate their voice quality on a visual analog scale of 0 (best) to 10 (worst). Videostroboscopy would be conducted on all patients to identify any anatomical and physiological changes, which included presence of laryngeal pathology, vocal fold closure pattern, and mucosal wave pattern.

Procedure-oriented outcomes include operation time, completeness of lesion removal, complications in Clavien-Dindo classification, length of hospital stay, disease recurrence rate, and reoperation.

Patient-oriented outcomes included peri-operative throat, nose, and overall discomfort in visual analogue scale, a 10-point scale with 0 (least uncomfortable) to 10 (most uncomfortable).

Medical costs of both interventions would be also calculated respectively, including costs for inpatient hospital stay, medical staff, operating theater and consumables.

Sample size calculation

Power calculation demonstrated that with a sample size of 21 per group, a two-arm study has a power of 80% to demonstrate a non-inferiority margin 7 absolute score, with one-sided significance of 0.05 regarding the primary outcome parameter, i.e. VHI-30. The calculation was based on published data from Misono et al.¹² in which a VHI-30 score over 16 was determined as a minimal important difference. Assuming a 20% drop-out rate, at least 54 patients were required, with 27 patients in each arm.

Participant timeline

TIMEPOINT	D1	Allocation	Post-allocation		Close-out

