	Pre-op assessment	Intra-operative	Immediate post-operative	FU at 2w, 6w, 3mo, 6mo, 1y	
Enrolment					
Eligibility screen	X				
Informed consent	X				
Randomization					
MLS		X			
TNLS		X			
Assessment					
Demographics	X				
	X				
	X				
	X				
	X				
	X				
Disease					
Type of lesion	X				
Site of lesion	X				
Size of lesion	X				
FL / Videostroboscopy	X		X		X
Anaesthetic assessment					
ASA	X				
Functional assessment					
VHI30	X				X
Other secondary voice-related outcomes (MPT, Acoustic analysis etc)	X				X
Procedural data					
Operation time		X		X	
Peri-op tolerance scale		X		X	
Peri-op pain score		X		X	
Post-operative outcome					
LOS			X		
Residual lesion			X		X
Complications			X		X
Recurrence					X
Reoperation					X
Pathology					X

Randomization

Patients are randomized to receive either MLS under general anesthesia or TNLS under local anesthesia. Block randomization is used to ensure equal distribution between two treatment arms. To avoid selection bias, the blocking mechanism is designed by a third party not involved in the study, and is not disclosed to investigators. Randomization is only performed on the day of recruitment, which the recruiter shall contact the third party for the result randomized treatment group. Both the patients and the laryngologists cannot be blinded due to the nature of operation.

Statistical method

All outcome measurements will be analyzed with an intention-to-treat principle. Independent samples t-test will be used for parametric continuous variables; Mann-Whitney U test will be used for non-parametric continuous variables; chi-square test will be used for categorical variables. A p-value less than 0.05 will be considered to be statistically significant. All statistical analysis will be performed using SPSS version 26.0.

Data monitoring and confidentiality

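### The trial is sized to show non-inferiority within 7 VHI-30 points, but the stated analysis is an ordinary difference test at p<0.05 that does not use the margin

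*Protocol*

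**What the plan says.** Three parts of the protocol bear on the primary analysis.

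- **Background.** The trial is set up with the "hypothesis that TNLS would be non-inferior to traditional microlaryngeal surgery".
- **Primary outcome and Sample size calculation.** The primary outcome is VHI-30: "The primary outcome was to compare the pre- and post-operative Voice-Handicap Index (VHI-30) of TNLS and MLS groups". For this outcome, 21 per group is said to suffice because "a two-arm study has a power of 80% to demonstrate a non-inferiority margin 7 absolute score, with one-sided significance of 0.05". Allowing 20% drop-out gives 27 per arm and 54 in total.
- **Statistical method.** For all outcome measurements, under intention-to-treat: "Independent samples t-test will be used for parametric continuous variables; Mann-Whitney U test will be used for non-parametric continuous variables", with chi-square tests for categorical variables. The only decision rule is "A p-value less than 0.05 will be considered to be statistically significant".

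The margin appears in the sample size paragraph and nowhere else. The Statistical method section has no confidence bound, shifted null hypothesis, statement of sidedness or separate rule for VHI-30.

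**The concern.** A t-test or Mann-Whitney test in its ordinary form has a null hypothesis of no difference. A non-inferiority test has a null hypothesis that TNLS is worse by 7 points or more. The two can disagree in either direction:

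- p>0.05 on the difference test is not evidence that the deficit is below 7, and it becomes more likely as the data get noisier or fewer.
- p<0.05 is not evidence that the deficit exceeds 7. A small but precisely estimated difference can be significant and still lie inside the margin.

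Two further mismatches follow. A bare p<0.05 is conventionally two-sided, whereas the sample size uses one-sided 0.05. And if VHI-30 is judged non-parametric, the plan moves to a Mann-Whitney p-value, which as specified cannot be compared with a margin in points.

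At stake is the trial's only stated hypothesis. Under the written rule, the 5% limit on falsely claiming non-inferiority is not enforced. Choosing a margin rule after the data are in would be post hoc, in a trial where neither patients nor laryngologists are blinded and the primary outcome is self-reported.

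**Working it through.** **Inputs from the protocol:** margin 7; one-sided alpha 0.05; power 80%; 21 evaluable per arm; 20% drop-out; 27 per arm recruited. **Not stated:** the SD and the assumed true difference. I take a true difference of 0 for sizing and read a higher VHI-30 as worse.

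**1. The plan's own sample size.**

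Drop-out: 21 / (1 − 0.20) = 26.25, rounded up to 27 per arm, 54 in total. This reproduces.

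The 21 cannot be checked directly without an SD, so I solve for the SD from n = 2·SD²·(z₀.₉₅ + z₀.₈₀)² / 7²:

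- SD = 7·√(21/2) / (1.645 + 0.842) = 9.12. The same formula with 20 gives 8.90, so any SD from just above 8.90 to 9.12 rounds up to 21.
- The noncentral t distribution gives 8.97.

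The figure of 21 is therefore consistent with a margin test at one-sided 0.05 and an SD of about 9.

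**2. What each rule concludes from an observed deficit (n = 21, SD 9).**

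SE = 9·√(2/21) = 2.777, with 40 degrees of freedom.

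- Two-sided difference test: non-significant up to 2.021 × 2.777 = 5.6 points.
- Margin test: non-inferior only if the observed deficit is below 7 − 1.684 × 2.777 = 2.3 points.

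An observed deficit between 2.3 and 5.6 points would be not significant, yet non-inferiority would not be shown. At SD 12 the first limit is 7.5 points, so even an observed deficit beyond the margin could be not significant.

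**3. Chance of a non-significant result when TNLS is truly 7 points worse.**

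The noncentrality parameter is 7/SE. The chance is P(|T| < t₀.₉₇₅), with T noncentral t.

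| SD | 21 per arm | 27 per arm | Margin test, false non-inferiority |
|---|---|---|---|
| 9 (implied) | 31% | 20% | 5% |
| 12 (assumed) | 55% | 44% | 5% |
| 15 (assumed) | 69% | 61% | 5% |
| 20 (assumed) | 80% | 76% | 5% |

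If p<0.05 is instead one-sided in the direction of TNLS being worse, the SD 9 figures are 20% (21 per arm) and 12% (27 per arm).

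**4. Effect of sidedness on the margin test (SD 9, true difference 0).**

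- 21 per arm: power 80% at one-sided 0.05, 69% at one-sided 0.025.
- 27 per arm: power 88% and 80%.

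**The case against.** The strongest reply has four parts.

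- **SAP territory.** The exact confidence-bound rule is often left to the SAP, which is not at hand. The sample size paragraph already gives margin, level and outcome, so the Statistical method section could be read as generic wording that leaves that specification in place. This does not remove the problem. The section does not defer or stay silent: it assigns tests and a decision rule to all outcomes, with no exception for VHI-30. An SAP with a margin test would have to depart from it.
- **Sidedness and misreading.** The protocol does not say that p<0.05 is two-sided, nor that p>0.05 will be called non-inferior. Both points stand. The percentages are conditional on that reading, and the one-sided reading lowers them. But the section offers no other route from the data to a conclusion on the hypothesis.
- **Full retention.** With 27 per arm the SD 9 figure falls from 31% to 20%, and the power lost at one-sided 0.025 is recovered. This is correct, but 20% is still four times the designed 5%, and the protocol itself plans for 20% drop-out.
- **Tests can be adapted.** A t-test can be run against a shifted null, and a rank test on shifted data or a Hodges-Lehmann bound can address a 7-point location shift. True, but the protocol specifies none of these. That an interval could be taken from the same data shows the remedy is cheap, not that the plan contains it.

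**Conclusion.** The concern holds. The hypothesis and sample size are non-inferiority with a 7-point margin; the prescribed analysis of the primary outcome is an ordinary difference test that does not refer to it. This is a wrong rule as written, not a detail left for later, and it must be fixed before analysis.

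If non-significance were taken as non-inferiority, the false-claim rate at the margin would be 31% with 21 per arm, or 20% with 27, against a planned 5%. These figures rest on a two-sided reading of p<0.05 and on an SD of 9 back-solved with a true difference of 0. Larger SDs, which are assumptions, give 55% to 80% with 21 per arm. The mismatch itself depends on none of these values.

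**What to change.** Give VHI-30 its own rule in the Statistical method section, for example:

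> For the primary outcome, TNLS is declared non-inferior to MLS if the upper limit of the two-sided 90% confidence interval (equivalent to a one-sided 95% bound) for the TNLS minus MLS difference in mean VHI-30 is below 7. The rule applies whatever the distribution; if the data are skewed, a bootstrap or robust interval for the mean difference is used.

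Restrict the t-test, Mann-Whitney U and chi-square tests to secondary comparisons, and state that their p<0.05 is two-sided. Add that a non-significant difference will not be interpreted as non-inferiority.

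The rule also needs a named visit and a choice between change from baseline and post-operative score. The protocol lists five follow-ups and fixes neither; that is a separate gap, best closed in the same amendment.

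The cost is a wording amendment. The rule uses the protocol's own margin and alpha, so 21 evaluable, 27 per arm and 54 in total stay as they are, and no extra data are needed.
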